**Table 2: Analysis Periods**

Phase	Period	Interval	
		From	To
Screening		00:00 on the date of signing the informed consent form	One minute prior to Dose 1 administration on Day 1
Regimen*	Post-dose 1	Date and time of Dose 1 administration	Minimum of: a) 23:59 on the date of last contact (for early study discontinuations) b) 23:59 on the date of relative Day 29 Post-dose 1 c) one minute prior to Dose 2 administration
Post-dose 1 FU		One minute after the end of the Post-dose 1 period	Minimum of: a) 23:59 on the date of last contact (for early study discontinuation or completion) b) one minute prior to Dose 2 administration
Regimen*	Post-dose 2	Date and time of Dose 2 administration	Minimum of: a) 23:59 on the date of last contact (for early study discontinuation or completion) b) 23:59 on the date of relative Day 29 Post-dose 2  Note: subjects who do not receive Dose 2 will not have a Post-dose 2 period.
Post-dose 2 FU		One minute after the end of the Post-dose 2 period	23:59 on the date of last contact (for early study discontinuation or completion)

**Note 1:** \* Regimen period includes both the Post-dose 1 and Post-dose 2 periods.

**Note 2:** FU = follow-up.

## 2.2. Pooling Algorithm for Analysis Centers

This study is conducted at multiple sites in 2 countries (ie, UK and France). The data from the countries and sites will be pooled (matching on cohort and vaccination schedule) for analysis.

## 2.3. Analysis Sets

### Full Analysis Set

The full analysis set includes all subjects who were randomized and received at least 1 dose of study vaccine (Ad26.ZEBOV, MVA-BN-Filo or placebo), regardless of the occurrence of protocol deviations.

### Immunogenicity Analysis Set

The immunogenicity analysis set includes all randomized and vaccinated subjects, who have at least 1 post-vaccination (ie, after the date of vaccination) evaluable immunogenicity sample.

### Per Protocol Analysis Set

The per protocol analysis set includes all randomized and vaccinated subjects, who received both the prime and boost vaccinations (administered within the protocol-defined window), have at least 1 post-vaccination (ie, after the date of vaccination) evaluable immunogenicity sample, and have no major protocol violations influencing the immune response.

The primary immunogenicity analysis will be performed on the per protocol analysis set. The analysis on the immunogenicity analysis set (including those subjects who received a late boost vaccination because of the study pause) will be included as sensitivity analysis to investigate the impact on the immune response. For the sensitivity analysis, subjects will also be categorized according to the actual Ad26.ZEBOV prime/MVA-BN-Filo boost interval as shown in [Table 3](#). In all cases for subjects who received Dose 1 (ie, only prime vaccination) but not Dose 2 while still continuing their planned visit schedule, the immune response measurements after the planned but not administered Dose 2 will not be included in graphs and tables showing descriptive statistics. These measurements will however be shown in listings, together with the indication that they are not used in the analysis.

**Table 3: Vaccination Schedules for Sensitivity Analysis**

Group	Group Label (Ad26.ZEBOV, MVA-BN-Filo)	Window (Days)
A	28-day interval	14-42
B	56-day interval	43-70
C	84-day interval	71-98
D	≥99-day interval	≥99

**Note:** the day of the prime vaccination is Day 1

### 2.4. Definition of Subgroups

There are 3 cohorts (each with Groups 1, 2 and 3) and Group 4 (UK: Cohorts I, II, and III; France: Cohorts II, III and Group 4) in this study. The subgroups that will be analyzed are shown in

[Table 4](#).

**Table 4: Cohort, Age Group Combinations and Parameters**

Study Cohort	Age Group	Analysis Parameters
Cohort I †	18-65 years	- Subject information - Safety
Group 4 ††	18-65 years	- Subject information - ELISA (units/mL) - VNA (IC 50 titers) - Safety
Cohorts II and III	18-65 years	- Subject information - ELISA (units/mL) - VNA (IC 50 titers) - ICS - Safety

Study Cohort	Age Group	Analysis Parameters
	18-50 years	- ELISA (units/mL)
	51-65 years	

† ELISA (units/mL), VNA (IC50 titers) and ICS are not assessed in Cohort I (ie, according to the CTP).

†† ICS is not assessed in Group 4 (ie, according to the CTP).

### 3. CHANGES TO THE PLANNED ANALYSIS

- Even in the absence of baseline immunogenicity samples, the post-baseline samples are of interest. Therefore, the immunogenicity analysis set is redefined to include subjects without baseline immunogenicity samples, provided that at least 1 post-vaccination evaluable immunogenicity sample is available for the subjects.
- Because different levels of post boost immunogenicity response are expected for different vaccination schedules, the per protocol analysis set is redefined to exclude subjects whose boost vaccination falls outside the protocol-defined window. Similar to the immunogenicity analysis set, the per protocol analysis set is also refined to include subjects without baseline immunogenicity samples.

### 4. INTERIM ANALYSIS AND DATA MONITORING COMMITTEE REVIEW

There was no interim analysis performed for this study. However, an independent data monitoring committee (IDMC) was instituted prior to the start of the study. The IDMC periodically reviewed safety data to ensure progressive safety of the subjects. Ad-hoc IDMC reviews of the safety data were also requested by the sponsor for any single event or combination of multiple events which were considered to jeopardize the safety of the subjects. See the IDMC charter and the associated SAP for further details.

For all cases of IDMC reviews, the data package and analysis results that could contain any piece of unblinding information were kept in a strictly confidential place, with access for IDMC and the independent statistical support group members only, until unblinding of the study by the sponsor.

### 5. SUBJECT INFORMATION

Subject information will be analyzed based on the full analysis set. The data will be presented separately for Cohort I and Group 4. For cohorts II and III, the presentation will be based on the pooled data (see

[Table 4](#)), unless otherwise specified.

#### 5.1. Disposition Information

The number and percentage of subjects randomized, vaccinated and entered in each analysis period will be tabulated. Subject assignment to vaccine regimen will be provided in a data listing (including the assigned regimen and the actual regimen received).

Furthermore, the number and percentage of subjects in the full analysis set who completed and those who discontinued together with the reason(s) for discontinuation will be tabulated and listed. This will be done for completion/discontinuation from study vaccination and from the trial.

## 5.2. Protocol Deviations

Subjects with protocol deviations will be identified prior to the database lock. The major protocol deviations will be summarized by the deviations category. A listing of the major protocol deviations will also be generated. The deviations that have the potential to influence immune response will be flagged in the listing.

## 5.3. Demographics and Baseline Characteristics

The demographic and baseline characteristics will be presented for the pooled Cohorts II and III data. Additionally, the data will be presented separately for each cohort and Group 4. The following demographic characteristics will be summarized.

- Sex (Female/Male)
- Age (years)
- Age group ( $\leq 50$  years versus  $> 50$  years)
- Race
- Ethnicity
- Country (UK versus France)
- Height (cm)
- Weight (kg)
- Body mass index (BMI,  $\text{kg}/\text{m}^2$ ), calculated from baseline height and weight

## 5.4. Prior and Concomitant Medications

The analysis of pre-study and concomitant therapies will be based on the World Health Organization (WHO) drug coded terms as provided in the clinical database. If the coded term for a concomitant medication is missing, then the reported term will be used and flagged in the table. The concomitant therapies will be tabulated per period. Additionally, a listing of all pre-study and concomitant therapies will be provided. There will be special attention to the use of analgesics/antipyretics (such as acetaminophen, non-steroidal anti-inflammatory drugs [NSAIDs] and aspirin) with onset during the first 8 days (start from the day of vaccination) following each vaccination.

Based on their start and stop dates, concomitant therapies will be reported in each analysis period during which they were applied. For missing or partial start/stop dates the following allocation rules will be applied:

- In case of partial start or stop dates, the concomitant therapy records will be allocated to analysis periods using the available partial information, without imputations. If, for example, only month and year are available, these will be compared to the month and the year of the analysis periods, and the concomitant therapy record will be allocated to the period(s) where these date parts match.

- In case of a completely missing start date, the concomitant therapy will be considered as having started before the trial.
- In case of a completely missing end date, the concomitant therapy will be considered as ongoing at the end of the trial.

**Remark:** In addition to the date information, time information is considered to allocate concomitant therapies to periods and/or phases, if available.

## 6. IMMUNOGENICITY

### 6.1. Endpoints

#### Secondary Endpoint:

Binding antibody levels elicited by vaccination using EBOV GP ELISA at 21 days post boost, as measured by ELISA (in ELISA units/mL).

#### Exploratory Outcomes:

Several exploratory objectives are specified in the CTP. Those objectives will be investigated for all corresponding available response outcomes, including the following:

- Humoral immune responses against EBOV GP as measured by:
  - ELISA (ELISA units/mL), at all available timepoints.
  - Neutralizing antibody response in titers that inhibit viral infection by a certain percentage (IC50), at all available timepoints.
- Cellular immune responses against EBOV GP as measured by:
  - Percentage of CD4+ T cells producing interferon (IFN)- $\gamma$ , tumor necrosis factor- $\alpha$  (TNF- $\alpha$ ) and/or interleukin (IL)-2 (using intracellular cytokine staining [ICS]), at all available timepoints.
  - Percentage of CD8+ T cells producing IFN- $\gamma$ , TNF- $\alpha$  and/or IL-2 (using ICS), at all available timepoints.

### 6.2. Immunogenicity Against the Insert

#### 6.2.1. Humoral Immune Responses

##### 6.2.1.1. Parameters

Humoral immune responses, as measured by the following assay, will be analyzed:

- **Binding antibody responses using Filovirus Animal Nonclinical Group (FANG) ELISA:** Quantification of antibodies binding to EBOV GP using the ELISA units/mL readout.

In addition, the following will be defined for ELISA (ELISA units/mL) binding antibody responses:

- **Sample interpretation:** A sample will be considered positive, if the value is above the lower limit of quantification (LLOQ).
- **Responder:**

- If sample interpretation is negative at baseline but positive post-baseline and the post-baseline value is greater than  $2.5 \times \text{LLOQ}$ ; OR
  - If sample interpretation is positive at both baseline and post-baseline and there is a greater than 2.5-fold increase from baseline (2.5-fold increase on the original scale).
- **Neutralizing antibody responses using virus neutralization assay (VNA):** titers of EBOV GP-specific neutralizing antibodies (unit: 50% inhibitory concentration [ $\text{IC}_{50}$ ]).

For VNA ( $\text{IC}_{50}$  titer) responses, the following will also be defined:

- **Sample interpretation:** a sample is considered positive if the value is greater than both the assay-specific LLOQ and  $3 \times (\text{amphotropic murine leukemia virus [aMLV]})$ . Otherwise, the sample is considered negative.
- **Responder:**
  - If sample interpretation is negative at baseline but positive post-baseline and the post-baseline value is greater than  $2 \times \text{LLOQ}$ ; OR
  - If sample interpretation is positive at both baseline and post-baseline and there is a greater than 2-fold increase from baseline (2-fold increase on the original scale).

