#### 6.2.1.2. Data Handling Rules

For ELISA binding antibody responses, values below the LLOQ will be imputed with  $\text{LLOQ}/2$ . For the calculation of fold increases, the values below LLOQ will be imputed with the LLOQ. For VNA titers, values less than the assay-specific LLOQ or less than  $3 \times \text{aMLV}$  will be imputed with half of the assay-specific LLOQ. For the calculation of fold increases, values that are less than the assay-specific LLOQ or less than  $3 \times \text{aMLV}$  will be imputed with the assay-specific LLOQ.

**Remark:** If an aMLV titer (negative control) is a censored value (ie,  $<40$ ), then it will be imputed with **40** before proceeding with further computations.

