#### 6.2.1.3. Analysis Methods

- The available humoral immune responses (immunogenicity against EBOV GP) will be evaluated for cohorts II and III. The pooled cohorts II and III data (ie, ELISA) will also be presented by age group. The Group 4 data will be presented separately. See

[Table 4](#) for more details.

Summary statistics (ie, geometric mean and corresponding 95% CIs) will be calculated and presented for ELISA binding antibody responses (ELISA units/mL) and VNA ( $\text{IC}_{50}$  titer) at each time point.

Regimen profiles of the geometric mean concentrations with 95% CIs will also be presented. In addition, graphs of the reverse cumulative distributions (ie, percentage of subjects versus the magnitude of the antibody response levels) will be provided for the following time points, if available:

- Baseline and pre-boost
- Baseline and 21 days post boost
- Baseline and 180 days post boost
- Baseline and Day 365 post prime

For both ELISA (ELISA units/mL) and VNA ( $IC_{50}$  titer), additional graphical representations (on a  $\log_{10}$ -scale) will be provided using dot plots (with distinction between positive and negative sample interpretations), by vaccination schedule.

Responder rates and positive sample interpretation will be summarized (ie, showing number, percentage and the exact 95% Clopper-Pearson CI) for ELISA (ELISA units/mL) antibody responses and VNA ( $IC_{50}$  titers) per time point.

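### The SAP's VNA responder rule does not guarantee a 2-fold rise in measured titre after a negative baseline, because positivity is judged against the larger of LLOQ and 3 × aMLV but the margin only against LLOQ

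*SAP*

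**What the plan says.** SAP 6.2.1.1 defines VNA sample interpretation with two limits: "a sample is considered positive if the value is greater than both the assay-specific LLOQ and" three times the aMLV titre. Any other sample is negative. A subject is a responder by one of two routes:

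- Baseline negative: "If sample interpretation is negative at baseline but positive post-baseline and the post-baseline value is greater than" 2 × LLOQ.
- Baseline positive: the post-baseline sample is also positive and "there is a greater than 2-fold increase from baseline (2-fold increase on the original scale").

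SAP 6.2.1.2 puts a floor under the negative control: "If an aMLV titer (negative control) is a censored value" (below 40), "then it will be imputed with 40 before proceeding with further computations". The same section sets the convention for fold changes: "For the calculation of fold increases, values that are less than the assay-specific LLOQ or less than" 3 × aMLV are replaced by the LLOQ.

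The ELISA rule in 6.2.1.1 has the same two-route form with a factor of 2.5, but its positivity limit is the LLOQ alone: "A sample will be considered positive, if the value is above the lower limit of quantification (LLOQ").

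On outputs, SAP 6.2.1.3 states: "Responder rates and positive sample interpretation will be summarized", with exact confidence intervals, for ELISA and VNA at each time point. SAP 6.1 lists VNA among the exploratory outcomes.

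**The concern.** In the ELISA rule the cut-off that makes a baseline negative is also the quantity multiplied to set the response threshold. Both routes therefore demand the same rise. The VNA rule keeps that form, but its baseline cut-off can lie well above the LLOQ while the response threshold stays tied to the LLOQ. The margin above the cut-off then shrinks, and it disappears once 3 × aMLV at the post-baseline visit reaches 2 × LLOQ.

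At stake is what a VNA responder rate means. Two subjects with similar titres can be held to different standards depending on which side of the cut-off the baseline fell. A nearly unchanged titre, or even a falling one if aMLV falls, can be labelled a response.

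**Working it through.** **Inputs.** All come from SAP 6.2.1.1 and 6.2.1.2, except the LLOQ. The SAP gives no number for it, so values from 20 to 150 are tried as an assumption. Each sample is taken to have its own aMLV titre, with a minimum of 40, so 3 × aMLV is at least 3 × 40 = 120. The plan states no figure for this rule that could be reproduced.

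**ELISA as comparator.** A negative baseline is at most LLOQ and the post-baseline value must exceed 2.5 × LLOQ. The rise therefore exceeds 2.5 × LLOQ / LLOQ = 2.5-fold, as in the baseline-positive route.

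**VNA, baseline negative.** The baseline is at most max(LLOQ, 3 × aMLV at baseline). The post-baseline value must exceed max(2 × LLOQ, 3 × aMLV post-baseline). The lower limit of the measured rise is

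max(2 × LLOQ, 3 × aMLV post) / max(LLOQ, 3 × aMLV baseline).

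The 2 × LLOQ test is redundant when 3 × aMLV post ≥ 2 × LLOQ, that is, when aMLV post ≥ (2/3) × LLOQ.

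| LLOQ (assumed) | aMLV 40 at both visits | aMLV 100 at both visits |
|---|---|---|
| 20, 40 or 60 | 120/120 = 1.0 | 300/300 = 1.0 |
| 80 | 160/120 = 1.33 | 300/300 = 1.0 |
| 100 | 200/120 = 1.67 | 300/300 = 1.0 |
| 120 | 240/120 = 2.0 | 300/300 = 1.0 |
| 150 | 300/150 = 2.0 | 300/300 = 1.0 |

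If aMLV falls from 100 to 40 at LLOQ 40, the limit is 120/300 = 0.40. A search over integer titres with aMLV 40, in steps of 10 for the LLOQ, found baseline-negative responders with a rise of 2-fold or less at every LLOQ from 20 to 110, and none from 120 to 160.

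**Worked subjects at LLOQ 40.**

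| Baseline → post | aMLV | Baseline status | Measured rise | Responder? |
|---|---|---|---|---|
| 115 → 125 | 40, 40 | negative (limit 120) | 1.09 | yes |
| 290 → 310 | 100, 100 | negative (limit 300) | 1.07 | yes |
| 290 → 130 | 100, 40 | negative (limit 300) | 0.45 | yes |
| 121 → 200 | 40, 40 | positive (limit 120) | 1.65 | no |

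**Chance of a false response.** Assume log10-normal assay error, a constant true titre, a fixed aMLV and a redundant 2 × LLOQ test. The SDs of 0.15 and 0.20 log10 are assumptions. With the true titre exactly at C, P(baseline ≤ C and post > C) = 0.5 × 0.5 = 25%. Requiring 2 × C instead gives 0.5 × (1 − Φ(0.301/SD)) = 1.1% (SD 0.15) to 3.3% (SD 0.20). With the true titre at half of C, the current rule gives Φ(0.301/SD) × (1 − Φ(0.301/SD)) = 2.2% to 6.2%. At one third of C, using 0.477 for 0.301, it gives 0.07% to 0.8%.

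**The case against.** The best defence is that the rule follows the SAP's own convention. A value below 3 × aMLV is treated as having no quantifiable EBOV-specific titre and is set to LLOQ for fold changes. On that scale, exceeding 2 × LLOQ is a 2-fold rise. This makes the rule formally consistent, but the convention itself turns 290 → 310 at LLOQ 40 into 310/40 = 7.8-fold. If 290 is indistinguishable from background, 310 against the same aMLV of 100 is weak evidence of response.

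Other points stand and limit the concern:

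- A reader might infer that subjects with non-specific neutralization are routinely counted as responders and that VNA rates are inflated. The documents do not support this. The post-baseline sample must exceed three times its own control, and only negative baselines at or above half the post-baseline value are affected. Neither the LLOQ nor the aMLV distribution is given, and enrolled subjects had no known Ebola exposure or Ebola vaccination.
- A reader might take 25% as the false-response rate. It applies only to a true titre exactly at the cut-off with a redundant 2 × LLOQ test, and falls quickly below it.
- A reader might extend the concern to reported fold increases. SAP 6.2.1.3 names no VNA fold-increase table, and the LLOQ imputation does not enter the baseline-positive route, which needs two positive samples.
- Reverse cumulative distributions, separate positivity rates and the placebo control would help to expose a material background effect.

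**Conclusion.** The inconsistency is real. After a negative baseline, the VNA rule guarantees a 2-fold measured rise only if 3 × aMLV at baseline does not exceed LLOQ, or if the post-baseline control happens to push the threshold high enough. With aMLV at its floor at both visits, that means an LLOQ of at least 120. If the LLOQ is lower, the gap is open to baseline-negative subjects generally, not only to those with raised background, because 3 × aMLV is never below 120. With aMLV 100 at both visits it is open across the whole LLOQ range tried.

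The consequence is modest. VNA responder rates are exploratory, no hypothesis is tested (SAP 1.3), and the secondary ELISA endpoint is unaffected. The size of any effect on the rates cannot be computed from the documents. The point warrants an inexpensive additional tabulation and does not cast doubt on the main results.

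**What to change.** Add a second VNA responder definition to SAP 6.2.1.1. For baseline-negative subjects, require the post-baseline sample to be positive and greater than 2 × max(LLOQ, 3 × aMLV at baseline). Leave the baseline-positive route as it is. At LLOQ 40 the threshold becomes 240 with baseline aMLV 40 and 600 with baseline aMLV 100, so none of the first three worked subjects qualifies and both routes require more than a 2-fold rise. Report this rate beside the current one, which is kept because the SAP's Amendment History gives alignment across the Phase 2 and 3 Ebola studies as a purpose. State the LLOQ as well.

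Do not change the fold-increase imputation to each sample's own cut-off. With LLOQ at most 120, a negative baseline with aMLV 40 (cut-off 120) and a negative post-baseline sample with aMLV 200 (cut-off 600) would give 600/120 = 5-fold from two negative samples. The present rule gives 1.0.

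The cost is SAP wording, one derived variable from aMLV data that the positivity rule already needs, and one extra tabulation. The responder rate may be lower. Some of that loss would be real rises: at LLOQ 40 and aMLV 40, a subject going from below 40 to 200 responds under the current rule but not under the added one (200 < 240). This is a further reason to show both rates.

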#### 6.2.1.2. Data Handling Rules

For ELISA binding antibody responses, values below the LLOQ will be imputed with  $\text{LLOQ}/2$ . For the calculation of fold increases, the values below LLOQ will be imputed with the LLOQ. For VNA titers, values less than the assay-specific LLOQ or less than  $3 \times \text{aMLV}$  will be imputed with half of the assay-specific LLOQ. For the calculation of fold increases, values that are less than the assay-specific LLOQ or less than  $3 \times \text{aMLV}$  will be imputed with the assay-specific LLOQ.

**Remark:** If an aMLV titer (negative control) is a censored value (ie,  $<40$ ), then it will be imputed with **40** before proceeding with further computations.

#### 6.2.1.3. Analysis Methods

- The available humoral immune responses (immunogenicity against EBOV GP) will be evaluated for cohorts II and III. The pooled cohorts II and III data (ie, ELISA) will also be presented by age group. The Group 4 data will be presented separately. See

[Table 4](#) for more details.

Summary statistics (ie, geometric mean and corresponding 95% CIs) will be calculated and presented for ELISA binding antibody responses (ELISA units/mL) and VNA ( $\text{IC}_{50}$  titer) at each time point.

Regimen profiles of the geometric mean concentrations with 95% CIs will also be presented. In addition, graphs of the reverse cumulative distributions (ie, percentage of subjects versus the magnitude of the antibody response levels) will be provided for the following time points, if available:

- Baseline and pre-boost
- Baseline and 21 days post boost
- Baseline and 180 days post boost
- Baseline and Day 365 post prime

For both ELISA (ELISA units/mL) and VNA ( $IC_{50}$  titer), additional graphical representations (on a  $\log_{10}$ -scale) will be provided using dot plots (with distinction between positive and negative sample interpretations), by vaccination schedule.

Responder rates and positive sample interpretation will be summarized (ie, showing number, percentage and the exact 95% Clopper-Pearson CI) for ELISA (ELISA units/mL) antibody responses and VNA ( $IC_{50}$  titers) per time point.

